3.3 Early Withdrawal of Subjects

3.3.1 Criteria for removal from study

Participants may voluntarily withdraw from the study at any time. The research team may also terminate the study if the participant does not meet the inclusion criteria or exhibits one or more of the exclusion criteria during the course of the study. For part 2 of the study, participants may be removed if they exhibit non-compliance to study procedures. Non-compliance is defined as 30 days without submission of an rPFT report if still eligible for rPFT reporting, or 3 months without a nurse coaching session if in the nurse coaching arm.

3.3.2 Follow-up for withdrawn subjects

The research team will follow up with withdrawn subjects to collect the research equipment. If the participant agrees, they will be given the endpoint assessment to document their reason for withdrawal. They may be asked to participate in a future focus group on subject experience in the study. There will be no additional follow-up. The withdrawn subjects may be replaced by another patient and caregiver from the recruitment waitlist.

4.0 Recruitment Methods

4.1 Identification of subjects

Potential patient participants will be identified by study staff of the Penn State Hershey ALS center at the time they are seen for routine visits to the Penn State Hershey ALS Clinic, or based on their responses to recruitment letters (see below). Potential subjects may also learn of the study by a flyer posted in the ALS clinic area. Practice control participants will be recruited from clinical staff. Respiratory therapists sought for participation in the study will be those providing respiratory therapy services to ALS patients in the clinic on the date of the study. The study will be listed on StudyFinder.

4.2 Recruitment process

Potential patients and caregivers will be approached by study staff of the Penn State Hershey ALS center at the time they are seen for routine in-person or telehealth visits to the Penn State Hershey ALS Clinic. In addition, a letter will be sent via mail or email to patients of the Penn State Hershey Medical Center ALS clinic, as well as those who are registered with the Greater Philadelphia chapter of the ALS

Association. A flyer will be posted in the clinic area informing patients of the study. Study information and contact information will be posted on Studyfinder.

Interested individuals will respond to a member of the study team who will follow up as in Section 4.4.

Practice control participants will be recruited from clinical staff by members of the study team.

Respiratory therapists will be approached by study staff prior to their first rPFT administration so that they may be delivered the SER and give verbal consent.

4.3 Recruitment materials

Potential patient participants may be mailed (see “Recruitment Letter” in Recruitment Materials) or emailed (see “Email Recruitment Letter” in Recruitment Materials) a recruitment letter. There will also be a flyer for the study posted within the clinic area (see “Study Flyer” in Recruitment Materials).

4.4 Eligibility/screening of subjects

Before enrolling prospective participants, we will contact the potential them by phone, email, or in person. For those individuals who are Hershey Medical Center patients, we will ask for their consent to access their medical record to confirm certain inclusion and exclusion criteria. For potential participants who are not treated at the Hershey Medical Center, we will request that they release medical records to us from their doctor. These will be reviewed by the study physician to confirm the diagnosis of ALS and other inclusion/exclusion criteria.

We will confirm that they and their caregiver are aware of the study requirements and are willing to complete the study procedures according to the procedures described (see “Screening questionnaire” in recruitment materials). This form addresses the remaining inclusion and exclusion criteria. In it, we will ask the patient if they anticipate any issues relating to performing spirometry or lack of devices or adequate internet access to participate (in the case of Part 2). They will be directed to an online internet speed test to ensure sufficient connection speed. We also ask if the caregiver anticipates they will be able assist in administering the procedure. If a caregiver is not available, a patient may be enrolled in the study if the investigator judges that they have the capacity to perform home PFTs unassisted. If at any point in the study a patient enrolled without a caregiver is no longer able to perform the home tests without additional assistance, a caregiver must be enrolled to aid home PFT administration, or the patient will be exited from the rPFT portion of the study.

Eligibility of respiratory therapists will be determined by their role in the Hershey Medical Center ALS clinic as well as their verbal consent to participate in the study.

5.0 Consent Process and Documentation

5.1 Consent Process

5.1.1 Obtaining Informed Consent

5.1.1.1 Timing and Location of Consent

A member of the study team will review the informed consent documents with the participants and receive their written consent to participate in the study. This consent procedure will take place only after initial screening procedures have been completed. This will take place either at the Hershey Medical Center ALS clinic, over the phone, or using the telemedicine interface between the clinic and the patient’s home.

Prior to any phone consent, participants will be provided with a physical or electronic copy of the informed consent document. The researcher attesting to the appropriateness of the consent process will complete the **Phone Consent Signature Page**. The patient will mail back the signed consent forms, and the member of the research team who explained the research will attach the completed Phone Consent Signature Page to the consent forms with the original signatures of the patient and LAR. The study team will then send the patient and LAR a copy of their signed consent form and the Phone Consent Signature Page for their records. Once the original signed documents are received by the study team, the participant may begin research procedures.

A member of the study team will deliver the summary explanation of research (SER) to participating respiratory therapists before their first clinical interaction in this study. The SER will be delivered at the Hershey Medical Center ALS Clinic.

5.1.1.2 Coercion or Undue Influence during Consent

Patients will be informed that the treatment they receive for ALS will not be affected by their choice to participate in the study. Explanation of the study and obtaining consent will be performed by a member of the research team who is not part of the clinical care team.

5.1.2 Waiver or alteration of the informed consent requirement

Partial waiver of consent is requested for pre-screening purposes.

5.2 Consent Documentation

5.2.1 Written Documentation of Consent

We will verify that we are using the most current IRB-approved version of the study specific consent form and that the consent form is in language understandable to the subject. Whenever possible, the consent form will be provided to the subject in advance of the consent discussion.

A member of the research team will review the informed consent documents with the prospective participants and receive their written consent to participate in the study described in this protocol. If performed over the phone or telemedicine interfaces, participants will sign a physical copy of the form and mail/email it to the research team. The patient and the caregiver, if available, will sign their own consent forms. This consent procedure will take place either in the ALS Clinic or over the telemedicine interface between the clinic and the patient's home. Written documentation of consent will be delivered after participants have been given an overview of the study's goals, procedures, risks, and benefits. Participants will receive a copy of the consent after it has been signed and dated by the person explaining the study.

5.2.2 Waiver of Documentation of Consent (Implied consent, Verbal consent, etc.)

Verbal consent will be obtained by the respiratory therapist participant before their first study session.

Verbal consent will also be obtained by participants via telephone to ask screening questions.

5.3 Consent – Other Considerations

5.3.1 Non-English Speaking Subjects

Non-English speaking subjects will not be enrolled.

5.3.2 Cognitively Impaired Adults

5.3.2.1 Capability of Providing Consent

The physician investigator will determine whether an individual is capable of providing informed consent. Cognitively impaired patients will not be enrolled in this study.

Due to disease progression, some subjects may not be able to physically sign the consent form, regardless of cognitive status thereby requesting LAR signature.

5.3.2.2 Adults Unable To Consent

The procedure outlined in HRP 013, "SOP: Legally Authorized Representatives, Children, and Guardians" will be followed to determine the legally authorized representative capable of providing informed consent. Written informed consent from the subject's LAR will be obtained before any study procedures take place.

5.3.2.3 Assent of Adults Unable to Consent

Subjects who are unable to sign the consent will be asked to provide verbal assent, which may be provided using an assistive communication device.

5.3.3 Subjects who are not yet adults (infants, children, teenagers)

5.3.3.1 Parental Permission

N/A

5.3.3.2 Assent of subjects who are not yet adults

N/A

6.0 HIPAA Research Authorization and/or Waiver or Alteration of Authorization

6.1 Authorization and/or Waiver or Alteration of Authorization for the Uses and Disclosures of PHI

Check all that apply:

- Not applicable, no identifiable protected health information (PHI) is accessed, used or disclosed in this study. [Mark all parts of sections 6.2 and 6.3 as not applicable]
- Authorization will be obtained and documented as part of the consent process. [If this is the only box checked, mark sections 6.2 and 6.3 as not applicable]
- Partial waiver is requested for recruitment purposes only (Check this box if patients' medical records will be accessed to determine eligibility before consent/authorization has been obtained). [Complete all parts of sections 6.2 and 6.3]
- Full waiver is requested for entire research study (e.g., medical record review studies). [Complete all parts of sections 6.2 and 6.3]
- Alteration is requested to waive requirement for written documentation of authorization (verbal authorization will be obtained). [Complete all parts of sections 6.2 and 6.3]

6.2 Waiver or Alteration of Authorization for the Uses and Disclosures of PHI

6.2.1 Access, use or disclosure of PHI representing no more than a minimal risk to the privacy of the individual

6.2.1.1 Plan to protect PHI from improper use or disclosure

Information is included in the “Confidentiality, Privacy and Data Management” section of this protocol.

6.2.1.2 Plan to destroy identifiers or a justification for retaining identifiers

The identifiers collected in the study and stored on REDCap will be maintained until the completion of the study, including analysis, and dissemination of results. Email addresses and phone numbers may be retained for those participants who are interested in participating in future research studies.

6.2.2 Explanation for why the research could not practically be conducted without access to and use of PHI

Certain PHI is used to maintain contact with the research subject through phone, mail, or email. Other PHI are variables related to the analysis of the study, such as date of birth, diagnosis, and gender. Voice recordings of the subject during coaching sessions will be used to assess quality and consistency of NRHC procedures. Voice recording of post-study focus groups will allow for easy transcription for analysis.

6.2.3 Explanation for why the research could not practically be conducted without the waiver or alteration of authorization

In order to be able to screen participants, we will need to access their medical record, either through the Hershey Medical Center EMR or through the release of records from an external care provider. We will access patients' medical records for the purpose of confirming the diagnosis of ALS before we admit them into the study and obtain consent. In order to contact patients, to describe the study and schedule the study visit, we will need access to phone numbers and email. Additionally, in the case of Study 2, we will need to know the patient's address to be able to ship the rPFT kit.

6.3 Waiver or alteration of authorization statements of agreement

Protected health information obtained as part of this research will not be reused or disclosed to any other person or entity, except as required by law, for authorized oversight of the research study, or for other permitted uses and disclosures according to federal regulations.

The research team will collect only information essential to the study and in accord with the ‘Minimum Necessary’ standard (information reasonably necessary to accomplish the objectives of the research) per federal regulations.

Access to the information will be limited, to the greatest extent possible, within the research team. All disclosures or releases of identifiable information granted under this waiver will be accounted for and documented.

7.0 Study Design and Procedures

7.1 Study Design

Part 1: This is a self-controlled study where each participant will be administered a standard of care PFT for measurement of FVC and MIP, as well as an rPFT, separated by at least an hour, for measurement of

experimental FVC and MIP. The rPFT is guided by a respiratory therapist in another room, utilizing the telemedicine interface of the Hersey ALS clinic and devices for measuring FVC and MIP (**Error! Reference source not found.**).

[figure not shown]

Figure 3: Tools for remote pulmonary testing. Left: Air Smart Spirometer and turbine. Right: respiratory pressure meter and mouthpiece.

Part 2: This is a two-arm, randomized study to determine 1) whether weekly monitoring of respiratory function can lead to timelier initiation of NIV and 2) whether structured nurse coaching leads to improved self-efficacy for managing disease and better maintenance of respiratory health. For enrollees in both arms, standard FVC and MIP measurements obtained approximately every three months by the respiratory therapist during ALS Clinic are supplemented with self-administered rPFTs performed weekly. To train the participant in the performance of rPFTs, a member of the research team will be present either in person or virtually to guide the patient and caregiver in the appropriate use of the equipment during the first four weeks of the study. Enrollees in the NRHC arm will additionally receive monthly coaching with the study nurse via telehealth. Approximately 5% of NRHC sessions will include audio recordings that will be evaluated by a second clinician nurse for quality and consistency.

rPFT protocol

Two devices are used to measure respiratory function:

- 1) Air Smart Spirometer, NuvoAir AB

The following information is paraphrased from the user manual, which is included in the “devices” page of the protocol.

The Air Smart Spirometer measures the forced vital capacity (FVC) in a forced expiratory maneuver. The Air Smart Spirometer is intended to be used by:

- Healthcare professionals trained to perform spirometry tests on patients.
- Adults trained by healthcare professionals or through self-learning who understand how to perform a high quality spirometry test.

The Air Smart Spirometer works iOS and Android devices. The Air Smart Spirometer has a built-in battery designed to function for at least 2 years or 1 000 single tests. The Air Smart Spirometer is designed to work with disposable and single use FlowMir® turbines. When performing a spirometry test, the user exhales into the turbine. The airflow generated sets a rotor in motion. The Air Smart Spirometer

registers the speed of the spinning rotor, converts it and transfers the data to the smartphone with the Air Smart Spirometer app.

The study subject will conduct 3-5 spirometry maneuvers to generate a forced vital capacity using the spirometer and associated application. Subjects may use the "Home Monitoring" version of the app, which requires the user to enter their date of birth, height, gender, and ethnicity. Alternatively, the "Clinical Trial" version of the application may pair the subject's smartphone to a cloud database hosted by Nuvoair using a subject-specific code. The coordinator will enter date of birth, height, gender, and ethnicity into the database, to which all spirometry recordings made by the subject will be synced.

2) NIF Meter NS 120-TRR, Instrumentation Industries

The following information is paraphrased from the user manual, which is included in the "devices" page of the protocol.

"The Instrumentation Industries, Inc. Negative Inspiratory Force (NIF) Meters are devices used to measure and monitor patient inspiratory effort. During use the NIF Meter is attached to the patient airway at a point that provides optimal readings of patient respiratory effort."

During each guided rPFT administration, a member of the research team and/or respiratory therapist will guide the patient and caregiver through three valid maneuvers of the FVC and MIP tests. The participants prepare the spirometer by connecting it to the tablet and opening the associated application. The patient is told to sit as upright as possible for the measurement of FVC. They will be told that to do this they will 1) inhale maximally, 2) exhale as hard and fast as possible, and 3) continue to exhale until indicated by the therapist. The researcher will also demonstrate this procedure to the patient. The caregiver applies nose clips to block airflow through the nose, holds the turbine of the spirometer to the patient's mouth and performs three repetitions of this sequence, with periods of relaxation between testings. Testing is repeated until three valid maneuvers are achieved. The application on the tablet computes the FVC and percentage predicted value, the best of which is retained.

To perform the MIP test, the participant inserts the mouthpiece into the pressure meter. The patient is told they will be asked to draw breath in as quickly and powerfully as possible, for at least one second. The researcher tells the caregiver to place a finger over the valve outlet so that no air flows through the mouthpiece during inhalation. Nose clips will be used. The patient performs three repetitions of this task. The maximal negative pressure from a valid run is recorded.

Each piece of reusable equipment will be labeled with an identification number. A log of all loaned materials will be maintained by the researchers. This log, included in the supporting documents, will be maintained on REDCap. Before delivery of the system to the study participant, each piece of equipment will be inspected and tested. This study will not collect prior medical therapy relevant to the use of the device. There are no restrictions on medicines or therapies used by the participants in this study.

Randomization (Part 2 only)

An unblinded blocked minimization method will randomize participants based on demonstrated factors affecting prognosis [Chio2009]. These include: time since diagnosis, age at consent, most recent FVC, and FVC slope from up to the previous year, if available.

NRHC protocol (Part 2 only)

Nurse Respiratory Health Coaching - The NRHC intervention follows the “teamlet” model described by Bennett et al. [Bennett2010], made up of the research coordinator who performs respiratory testing, and the nurse practitioner using an ALS-tailored variant of the GROW model. 5 percent of NRHC sessions will undergo audio recording and be reviewed by a nurse-researcher on the study team.

- Goal setting - Discuss patient-driven goals for the session as well as for short and long term respiratory management for the patient/caregiver dyad.
- Reality Check - Explore current situation. Review PFT results and answers to the respiratory questionnaire. Share information and gently challenge assumptions that may present barriers to goal attainment.
- Options - Identify options and alternative strategies, including NIV, Cough Assist, Nebulizer, and Breath Stacking. Discuss patient and system barriers to pursuing these options.
- Wrap-up - Coach dyad towards implementing endorsed plan with a focus on trouble-shooting barriers and enhancing facilitators to successful implementation. Address what is to be done and by whom.

Those randomized to the coaching arm will receive brief coaching checkups from another nurse on the study team who is not the coach. These will occur during the 4th and 8th months after randomization, and at study exit. The nurse performing the checkup will guide the participant to reflect on the coaching process, using prompts provided in the Focus Group template. Coaching checkups will be by phone or via Penn State Health Zoom videoconferencing. Audio of these sessions may be recorded.

Focus groups (Part 2 only)

Focus groups may be convened comprised of subjects who have completed the study. Focus groups will ask subjects to reflect on their experiences in the study regarding the use of technology, nurse coaching, and any behavioral changes observed. Focus groups will be conducted either at the location of the Hershey ALS Clinic or via Penn State Health Zoom videoconferencing. Audio recordings of the focus groups will be captured.

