7.2 Study Procedures

7.2.1 Part 1

On or before the date scheduled for Study 1, a member of the research team who is not part of the ALS clinical team will describe the procedures and receive written informed consent from the patient and caregiver dyad, as well as the respiratory therapist. The participant team undergoes the initial in-person pulmonary function testing, followed 2-3 hours later at the end of the clinical visit by the rPFT. rPFT administration is described in Section 7.4.2. For roughly half of the enrolled participants, the order of assessments is reversed. Following the study procedures, the therapist and patient/caregiver dyad will complete a survey concerning the ease of use and confidence in the rPFT assessment.

Part 1 includes the recruitment of up to 20 practice control participants for validation of the study procedures. They will perform the same procedures as the patient and caregiver, in conjunction with the respiratory therapist.

7.2.2 Part 2

Following consent, the researcher will collect demographic and clinical information: date of birth, gender, time since symptom onset, ALSF Functional Rating Scale - Revised, PFT history, and region of symptom onset. The researcher will guide the subject through completion of the respiratory health questionnaire and self-efficacy assessment.

Subjects consented on the day of their in-person clinic visit will be sent home with an rPFT kit and scheduled for weekly training appointments with a member of the research team. For patients consented remotely, the research team will ship a kit and schedule them for weekly training appointments.

The weekly schedule following the first site visit at week 0 is shown in **Error! Reference source not found.** Weekly training sessions will be guided through the telehealth interface by a member of the research team. If by the 4th training session the participant is able to complete rPFT procedures without guidance as determined by the researcher-completed aptitude assessment, and achieve an FVC result within 10% of the average value from the first three sessions, the participants will be randomized to one of the two study arms.

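### Minimisation is specified with no random element, block definition or concealment and directly follows a partly subjective check, which leaves the Aim 2 comparison open to selection

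*Combined protocol and SAP*

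**What the plan says.** The whole randomisation text is in Section 7.1, under Randomization: "An unblinded blocked minimization method will randomize participants based on demonstrated factors affecting prognosis". The factors are "time since diagnosis, age at consent, most recent FVC, and FVC slope from up to the previous year, if available". No assignment probability, block size or meaning of blocked, factor categories, weights, tie rule or rule for a missing slope is given. Nothing says who runs the allocation, in what system, or whether it is concealed. Section 8.3 (Statistical methods) adds nothing and names no covariates for the Aim 2 mixed model.

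Section 7.2.2 (Part 2) makes randomisation conditional on two things at the fourth training session. The participant must be "able to complete rPFT procedures without guidance as determined by the researcher-completed aptitude assessment", and must "achieve an FVC result within 10% of the average value from the first three sessions". If both hold, "the participants will be randomized to one of the two study arms".

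On who knows what, Section 7.2.2 says that "the researcher will collect demographic and clinical information", including date of birth and PFT history. These give age and the two FVC factors. Time since diagnosis is not on that list, but Section 4.4 has medical records reviewed to confirm the diagnosis. The coaching team is described in Section 7.1 as "made up of the research coordinator who performs respiratory testing, and the nurse practitioner". Section 18.0 marks multi-site research as not applicable.

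**The concern.** Minimisation with no random element assigns each participant from the factor values and the record of past allocations. Blocking, if it means fixed blocks, makes the last places in each block certain. Here the allocation comes straight after a decision that rests in part on a researcher's opinion, in a single-site open trial. Research staff collect or can look up the factor values, and the coordinator who does the testing belongs to the coaching team and so knows who is coached. Nothing in the plan separates the person who completes the aptitude form from the allocation record.

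An assessor who can anticipate the next arm may, without meaning to, pass or hold back a borderline participant accordingly. Both arms do weekly home testing, so coached versus uncoached (Aim 2) is the only comparison that randomisation protects. Its primary outcome is self-reported self-efficacy, which could plausibly be related to how readily a participant masters the tests.

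**Working it through.** The plan gives no figure for predictability, so there is none to reproduce. The check asks how often an informed guess of the next arm would be right under each reading the text allows.

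**Inputs from the plan**
- Four minimisation factors (Section 7.1).
- 40 completers and up to 60 enrolled (Sections 8.1 and 16.2); both numbers were simulated.
- 1:1 allocation, implied by the 20 coached subjects in Section 7.2.2.

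**Assumptions, not in the plan**
- Two or three equally likely, independent levels per factor.
- Probability *p* of assigning the favoured arm: 1.0, 0.9, 0.8 or 0.7.
- 600 simulated sequences per setting.

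**Step 1: sequential minimisation, assessor sees all tallies.** For each newcomer, add over the four factors the number of earlier participants in each arm who share the level. The arm with the smaller sum is favoured, and ties are tossed. If a share *f* of newcomers has a favoured arm, the correct-guess rate is

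g = f × p + (1 − f)/2.

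With p = 1, f was 0.814 to 0.837, so 81–84% of allocations are fixed in advance. For N = 40 and two levels, g = 0.828 × 1 + 0.172/2 = 0.914 (simulated 0.913). Across settings g was 0.909 to 0.919.

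**Step 2: same method, assessor knows only arm totals.** Guessing the smaller arm was right 0.678 to 0.718 of the time.

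**Step 3: blocked read as permuted blocks of 2m.** The share of certain allocations is 1/(m + 1). The correct-guess rate is [m + (4^m / C(2m, m) − 1)/2] / 2m.
- Blocks of 2 (m = 1): certain 1/2; g = [1 + (4/2 − 1)/2]/2 = 0.75.
- Blocks of 8 (m = 4): certain 1/5; g = [4 + (256/70 − 1)/2]/8 = 5.329/8 = 0.666.

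Simulation agreed (0.750 and 0.665).

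**Step 4: blocked read as joint allocation of batches.** With N = 40 and continuous factors, a simple guess from the factors and current imbalance was right 0.731, 0.675 and 0.568 of the time for batches of 2, 4 and 8.

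**Step 5: effect of a random element.** With p = 0.8, N = 40 and two levels, g = 0.866 × 0.8 + 0.134/2 = 0.760 (simulated 0.761).

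| Assessor's knowledge | p = 1.0 | p = 0.9 | p = 0.8 | p = 0.7 |
|---|---|---|---|---|
| All tallies | 91–92% | 83–85% | about 76% | about 68% |
| Arm totals only | 68–72% | 65–69% | 62–64% | 58–61% |
| No past allocations | 50% | 50% | 50% | 50% |

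**Step 6: from predictability to bias.** Suppose a share *q* of candidates is borderline, their outcome differs by *D* standard deviations, and every one of them is passed or failed by predicted arm. The bias is then about q × (2g − 1) × D. The factor (2g − 1) runs from 2 × 0.57 − 1 = 0.14 to 2 × 0.91 − 1 = 0.82 across the readings. The documents give neither q nor D, so the calculation stops there.

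**The case against.** A reader might infer that staff can foresee most allocations. The documents do not support this as a statement of fact. It needs deterministic sequential minimisation and an assessor who sees the tallies, and neither is stated. The text says the method will randomise. Unblinded may mean only open-label, since coaching cannot be hidden from its recipients. Predicting an arm from the factors also needs cut-points, weights and a missing-slope rule that are not given. Under a block reading, only 50% down to 20% of allocations are certain. All of this stands, and the 80% and 90% figures must be read as conditional.

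The check is also not purely subjective: nobody can be passed on opinion alone if the FVC condition fails. That stands too and confines discretion to the aptitude form.

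A reader might put a figure on the bias in standard deviations, or say that analysis can do nothing about it. Neither holds. Any such figure rests on assumed values of q and D, and the check concerns testing technique while the outcome is change in self-efficacy. Self-efficacy is measured before the check and Section 8.3 analyses change from baseline, so measured baseline differences are at least partly handled. Unmeasured differences are not.

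Finally, an 0.8 coin alone still leaves a fully informed guess right about 76% of the time, no better than the block readings. This is correct, and it is why the remedy must also limit what the assessor knows.

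**Conclusion.** The concern holds in conditional form. The plan specifies minimisation with no stated random element, block definition, operator or concealment, and runs it directly after a check that is partly a researcher's assessment and partly numeric. In the worst case the text allows (deterministic, sequential, tallies visible to the assessor), about 80% of allocations are fixed and about 90% can be guessed. Under block, batch or totals-only readings a guess is right about 57–75% of the time. Every figure above 50% requires the assessor to know something of past allocations. The plan does not say that the assessor has this knowledge, but nothing in it prevents it, and the staffing makes it plausible.

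The exposure is to selection in Aim 2. Its size cannot be derived from the documents, and adjustment can only partly remove it. The percentages rest on 1:1 allocation and assumed factor distributions. They changed little between two and three levels or between 40 and 60 participants.

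**What to change.** Amend Sections 7.1, 7.2.2 and 8.3 as follows.

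- Replace the undefined blocks with minimisation that has a stated random element, for example probability 0.8 to the balancing arm. Give the factor categories, the tie rule and the rule for a missing FVC slope.
- Lock the aptitude form and the fourth-session FVC in REDCap before an allocation can be requested.
- Have the system, or someone other than the assessor, generate the allocation.
- Keep the tallies and, as far as possible in a small team, past allocations from the assessor. Without this the coin leaves about 76% predictability; with only arm totals known the rate is 62–64%, and with nothing known it is 50%.
- Report how many participants fail the check, on which condition, and their baseline data.
- Include the minimisation factors as covariates in the Aim 2 mixed model.

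The cost is randomisation set-up in a system the study already uses, a short protocol amendment, and some care over who assesses whom. Balance on the four factors will be slightly looser, which the covariates largely recover.
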